**Table 4. Teleassessment Equipment for the Enhancement Study**

PDDS Level	Equipment
PDDS 0-4	Chromebook CAMRY Digital Hand Dynamometer Grip / 90 Kgs A&D Medical Wrist Blood Pressure Monitor SumVibe Soft Tape Measure 120 Inches American Challenge Soccer Mini Disc Cone Wall tape Paper indicating 5" line
PDDS 5-7	Chromebook CAMRY Digital Hand Dynamometer Grip / 90 Kgs A&D Medical Wrist Blood Pressure Monitor

PDDS: Patient Determined Disease Steps.

### Potential covariates

In addition to age, sex, education-level, height, and race, which were collected at baseline, information on all participants' time-varying covariates were collected through a questionnaire at baseline and the three follow-up time points. These covariates included: weight, type of MS, prescribed and non-prescribed medications, distance from the clinic

(address), caregiver support, assisted devices, PDDS. The type of MS, PDDS, age and geographic locations based on participants zip code (urban/non-urban) were our prespecified moderators for the study outcomes.

## Sample Size Calculations and Study Power

For the Main study an *a priori* power analysis was conducted based on sample size estimation for longitudinal designs with attrition with at least 30 sites. Based on the conservative power and sample size calculations, the project was powered for a minimum of 533 participants completing the study with an assumption of a 35% attrition rate; therefore, a total estimated sample size of 820 was needed to detect a between group effect. We assumed intent to treat analyses, 80% power, two-sided family-wise error rate of 0.05, intra-class correlation of 0.05, and a correlation of 0.3 among repeated measures. We also assumed an attrition rate of 35% and a small minimally detectable effect size of 0.2. We make a conservative assumption that the correlation between repeated measures would be 0.3. We have four primary and four secondary outcomes and hence the sample size was estimated after accounting for multiple testing and with a type 1 error rate of 0.00625 for each hypothesis test.

[figure not shown]
For the Enhancement study, we assumed ANCOVA with a pre-post correlation of 0.7, 80% power, one-sided test with statistical significance of 0.05, and attrition rate of 25%. Further, these sample size calculations assumed a non-inferiority margin of -4 units for MFIS, where fatigue is one our key primary outcome identified by the stakeholders in our project. A change of 4 or greater has been found clinically meaningful for quality of life. Based on these assumptions a sample size of 55 completers in rDirectCAM were needed and with an attrition

rate of 25%, we needed 74 participants in rDirectCAM.

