## Analytical and Statistical Approaches

### **Main Study**

Our analysis was following ITT protocol as all participants assigned to the randomized clinics and completed baseline assessment were included in the analysis.

Our primary hypotheses were about comparing the change in the 11 outcomes (listed in **Table 4**) between baseline and 12th month follow-up across the two arms. We considered these 11 hypothesis tests for the 11 outcome variables as part of a single family of hypotheses. We employed the Holm-Bonferroni method for controlling the overall family wise error rate and computed adjusted *p*-values. For each outcome we used a linear mixed effects model, with TeleCAM arm as the reference category, and accounting for the correlated nature of the data due to the nesting of participants within a clinic as random effects. Crude models included fixed effects included both Arms (TeleCAM, DirectCAM), Time (baseline [reference], 3 month, 6 month, 12 month), an Arms X Time interaction, and accounted for randomization strata (clinic location being urban vs. non-urban). The interaction of Arms and Time variables was the primary effect of interest since it quantified the differences within Arm change in the outcome from baseline over time of the two Arms. For example, based on the fitted model that included the interaction between Arm and Time, the difference in change over time from baseline to 12 months between DirectCAM and TeleCAM were estimated. Contrast statements were used to test the null hypotheses in conjunction with the fitted model coefficients and standardized differences in the average treatment effect reported. The estimates of the change in health and function outcomes for each arm and their 95% confidence interval were also reported. As a sensitivity analysis, similar models additionally adjusted for sex, race, and post-COVID data collection measure indicated were also ran. Note that, since post-COVID, data collection for patient reported outcomes was conducted remotely for remaining participants, the former was also included as a covariate in the adjusted model. Next, missingness in primary and secondary outcomes were addressed using multiple imputation technique (MCMC) via PROC MI in SAS,

assuming missing at random. Additional sensitivity analyses were conducted using wild bootstrap to assess the robustness to model assumptions.

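### The stated 80% power for an effect of 0.2 is not tied to a metric or contrast, does not reach 80% on the month-12 change test if 0.2 is in SD units, and uses 8 tests where the analysis uses 11

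*Combined protocol and SAP*

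**What the plan says.** In the combined protocol and SAP, Sample Size Calculations and Study Power gives the Main study's basis as "sample size estimation for longitudinal designs with attrition with at least 30 sites". It goes on: "We assumed intent to treat analyses, 80% power, two-sided family-wise error rate of 0.05, intra-class correlation of 0.05", with a correlation of 0.3 among repeated measures, which it calls conservative. It adds: "We also assumed an attrition rate of 35% and a small minimally detectable effect size of 0.2". The result is 533 completers and 820 enrolled. On multiplicity it says "We have four primary and four secondary outcomes and hence the sample size was estimated after accounting for multiple testing", which gives 0.00625 per test. The target is described only as a between-group effect. A figure that is not shown follows the paragraph.

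Analytical and Statistical Approaches, Main Study, defines the primary hypotheses as change from baseline to month 12. It fits an arm-by-time mixed model from which "the difference in change over time from baseline to 12 months between DirectCAM and TeleCAM were estimated". Clustering enters as "nesting of participants within a clinic as random effects". The analysis set is inclusive: "all participants assigned to the randomized clinics and completed baseline assessment were included in the analysis". On multiplicity: "We considered these 11 hypothesis tests for the 11 outcome variables as part of a single family of hypotheses", with Holm-Bonferroni. The same section later counts five primary and six secondary outcomes.

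**The concern.** A power statement applies to one contrast, one effect metric and one alpha. Here the text leaves the first two open, and the third differs from the alpha the analysis uses.

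A reader will naturally take a small effect of 0.2 as 0.2 SD on the primary test. A difference in change is a noisy contrast when the repeated-measures correlation is only 0.3, so 80% power for 0.2 SD with 533 completers looks out of reach.

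What is at stake is interpretation. The trial compares two ways of delivering the same programme, so a non-significant difference could easily be read as showing similarity. A claim that 0.2 was detectable with 80% power would support that reading more strongly than the design allows.

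**Working it through.** **Inputs from the plan.** Power 80%; two-sided alpha 0.00625; correlation 0.3; ICC 0.05; attrition 35%; 533 completers; 820 enrolled; at least 30 sites; 11 tests in the analysis family. The Enhancement study's sizing, in the same section, uses a pre-post correlation of 0.7.

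**Assumptions.** 1:1 allocation. A constant clinic effect (random intercept), which cancels from change. For the all-enrolled figures, retention of 88%, 77% and 65% at months 3, 6 and 12; only the 65% follows from the plan.

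**1. The plan's own figures.**
- 533/0.65 = 820 and 0.05/8 = 0.00625, so both reproduce.
- 533 itself does not follow from the stated inputs if 0.2 is in outcome SDs. Without any clustering, the totals needed are 608 for the mean of four visits, 1,280 for a single visit and 1,792 for change.
- Several other routes come close to 533:
  - d = 0.4, baseline-adjusted, 30 sites: design effect 1 + (533/30 − 1) × 0.05 = 1.838, power 79.8%.
  - f = 0.1 in a 3-df arm-by-time test with the same design effect: power 79.2%.
  - d = 0.2 on the four-visit mean, one-sided 0.00625, no ICC: exactly 533.
- These routes use different contrasts, so the text does not identify the one intended.

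**2. Month-12 change contrast, 0.2 in outcome SDs.** For completers, SE = √[2(1 − ρ) × 4/533] and power = Φ(0.2/SE − z), with z = 2.734 at 0.05/8 and 2.838 at 0.05/11. The all-enrolled SE comes from generalised least squares on the four visit means per arm, with exchangeable correlation ρ.

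| ρ | Analysed | SE | Power at 0.05/8 | Power at 0.05/11 |
|---|---|---|---|---|
| 0.3 | 533 completers | √(1.4 × 4/533) = 0.1025 | Φ(1.951 − 2.734) = 21.7% | 18.8% |
| 0.3 | all 820 | 0.0953 | 26.2% | 23.0% |
| 0.7 | 533 completers | √(0.6 × 4/533) = 0.0671 | Φ(2.980 − 2.734) = 59.7% | 55.7% |
| 0.7 | all 820 | 0.0637 | 65.8% | 61.9% |

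Moving all dropout before month 3 or after month 6 changes the 26% by less than one percentage point. With 533 completers, 80% power at 0.05/8 would need a correlation of about 0.79.

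**3. Other metrics for 0.2, 533 completers, 0.05/8.**
- SDs of change: 0.2/√(4/533) = 0.2/0.0866 = 2.309, and Φ(2.309 − 2.734) is about 34%.
- Cohen's f = 0.2, so d = 0.4 in outcome SDs, ρ = 0.3: 0.4/0.1025 = 3.902, and Φ(3.902 − 2.734) is about 88% (about 86% at 0.05/11).

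**4. Effect detectable with 80% power at 0.05/11.** (2.838 + 0.842) × SE, with the sum 3.679 before rounding:
- ρ = 0.3: 0.38 SD (completers), 0.35 SD (all enrolled).
- ρ = 0.7: 0.25 SD (completers), 0.23 SD (all enrolled).

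**5. Eight tests against eleven.** A test with exactly 80% power at 0.05/8 has Φ(3.576 − 2.838) = 77% at 0.05/11, the first Holm step.

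**The case against.** The strongest reply is that the calculation may be sound for a contrast and metric that cannot be seen here. The missing figure may define both, and under a Cohen's f reading the power does carry over to the primary test at about 88%. Study Overview also speaks of small to moderate effects. This stands, so the point is conditional on 0.2 being in SD units. A reader might infer that 533 is an arithmetic error; the documents do not show that.

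The correlation of 0.3 is described as conservative, and for a change contrast a low value is the pessimistic direction. That also stands, and it is why 22 to 26% must not be quoted alone. The document's own 0.7 raises power to 60 to 66%. That is still short of 80%, and applying 0.7 to month 12 is itself an assumption.

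The 8-versus-11 gap has a likely explanation. Study Outcomes names four primary domains (fatigue, pain, quality of life, physical activity) and four secondary ones (balance, endurance, gait, strength), whereas the analysis counts instruments. It also says that the Timed 25-Foot Walk was not counted for power. This explains much of the mismatch without removing it. A reader might infer inflated family-wise error; Holm over 11 tests still controls it.

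A reader might also carry the ICC of 0.05 over to change scores, which would give roughly 10 to 12% power with completers and detectable effects of 0.46 to 0.51 SD. The documents state no clinic ICC for change, so those are not design figures.

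Finally, the confidence intervals and the comparisons with published minimally important differences will show the actual precision. They will, but beside a design claim that does not describe the same test.

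**Conclusion.** The point holds as a conditional one and should be fixed. The text ties 80% power to an effect of 0.2 without saying what 0.2 measures or which contrast it refers to. On the primary month-12 change contrast, none of the SD readings examined reaches 80% at alpha 0.00625: 22 to 26% in outcome SDs at the stated correlation, about 34% in SDs of change, and 60 to 66% in outcome SDs at a correlation of 0.7. The one reading that does, Cohen's f, means 0.4 SD. All of this assumes 1:1 allocation and clinic effects that cancel from change; power would be lower if change varied by clinic. The 8-versus-11 mismatch is explicit but small, 80% to 77% at the first Holm step. No estimate or test is invalid, and the consequence is confined to how a null result is read.

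**What to change.** Leave the sample, estimates and tests as they are, and keep the a priori calculation on record. In Sample Size Calculations and Study Power:

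- State the metric of 0.2 and the contrast for which 533 was computed.
- Note that the calculation used 8 tests while the analysis family has 11, and that Holm still controls family-wise error.
- Add the effect detectable with 80% power on the month-12 change contrast at 0.05/11, as a range: about 0.38 SD (533 completers) or 0.35 SD (all 820, assumed dropout) at correlation 0.3, and about 0.25 or 0.23 SD at 0.7.
- Say that these figures assume clinic effects cancel from change and would be larger otherwise. Do not add 0.46 to 0.51 SD as a design figure.

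Read null results against that range and the confidence intervals, not against 80% power for 0.2. Two editorial corrections belong with this: the Main Study analysis text refers to Table 4 for its outcomes, but Table 4 lists equipment; and the Timed 25-Foot Walk is called exploratory in the text but sits with the secondary gait measures in Table 3.

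The cost is a few sentences and a less favourable stated figure.

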## Time Frame for the Study

For the Main study, TEAMS launched its participant recruitment in October 2017 and ended participant enrollment in 2019. **Figure 4** shows the timeline for a few of the major milestones completed during the study period. Recruitment for the rDirectCAM group (Enhancement study) was not necessary as we had interested participants who already signed up the study via our website or through our clinic partners but were not able to enroll before the Main study needing to be ceased due to the pandemic. We established a protocol for conducting the teleassessments and tele-training and developed a structured set of procedures for equipment purchase and shipping/scheduling based on the Enhancement supplement received in May 2020. We began participant screening for the Enhancement study on September 10, 2020, with 100% enrollment completed on March 22, 2021. The study was closed on November 1, 2021.

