### **Enhancement Study**

We used a quasi-experimental design to compare rDirectCAM with DirectCAM. Our hypothesis posits that the observed difference in outcome effects between rDirectCAM and DirectCAM is less than a predetermined non-inferiority margin ( $-\Delta$ ). These margins were selected based on the MCID or minimal detectable change (MCD) of the studied outcomes among MS population published in literature (MFIS= 4, BBS= 3, TUG= 10.6, FTSTS= 13, Grip-strength= 10.5, SF-36 Physical functioning= 7.1 and SF-36 pain= 4.9).

Specifically, we hypothesized that the effect of rDirectCAM was not inferior to that of DirectCAM by a margin that was considered clinically acceptable, thereby affirming the non-inferiority of rDirectCAM in comparison to DirectCAM. In other words, if the resulting *p*-value was significant, this would mean that we rejected the null hypothesis which stated that the difference in the effect between two arms were more than the non-inferiority margin. Statistical significance level of 0.05 and at confidence interval 95%, same as superiority trials,

was applied to determine non-inferiority. To achieve a balance between the study arms, several analyses involved regression-based parametric adjustment measures that are sensitive to model misspecification. Propensity scores are another widely used measure to achieve balance or matching between the study arms. These scores model the probability of being assigned to the given treatment conditional on observed baseline covariates obtained via measures including matching, inverse probability treatment weighting (IPTW), and stratification and covariate adjustment. Matching-based measures such as nearest neighbor matching algorithm often led to study participants being excluded when a match was not available. This may have potentially biased the effect estimates. When this occurred, we utilized stabilized IPTW, a non-parametric balancing strategy, to achieve balance between the two study arms (rDirectCAM and DirectCAM). Using this weighted analysis, we modeled the causal parameter as the inverse of the conditional probability of receiving the treatment given the observed covariates, a technique that provides asymptotically unbiased estimates and uses data on all available study participants across the two arms.

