Our general analytic approach was to leverage the linear mixed modeling framework to account for repeated nature of data. Appropriate contrasts were applied using the fitted model. Sensitivity analyses were performed to assess distributional and other modeling assumptions. Missing data was imputed using multiple imputation where necessary. The non-inferiority ( $-\Delta$ ) of the rDirectCAM was assessed by comparing the lower limit of confidence interval for each outcome to its corresponding margin so that if the lower bound was above this margin, then the rDirectCAM was deemed non-inferior. For the MFIS and TUG assessments, wherein an elevated score signified a deterioration in the outcome, we juxtaposed the upper limit of the

confidence interval against a predefined margin. Non-inferiority was deemed established when the upper bound was less than  $-\Delta^{133}$ .

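### Enhancement study: sized for a one-sided 0.05 test, but non-inferiority is judged on one limit of an unlabelled 95% interval; if that interval is two-sided, power is about 70%, not 80%

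*Combined protocol and SAP*

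**What the plan says.** All references are to the combined protocol and SAP.

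- **Sizing.** Under Sample Size Calculations and Study Power, the Enhancement study assumes "80% power, one-sided test with statistical significance of 0.05, and attrition rate of 25" (per cent), with a "non-inferiority margin of -4 units for MFIS". For the model, "we assumed ANCOVA with a pre-post correlation of 0.7". The result is 55 completers in rDirectCAM, or 74 enrolled.
- **Decision level.** Under Analytical and Statistical Approaches, Enhancement Study, the level is "Statistical significance level of 0.05 and at confidence interval 95%, same as superiority trials". A significant p-value is taken to mean that "we rejected the null hypothesis which stated that the difference in the effect between two arms were more than the non-inferiority margin".
- **Interval rule.** The same section judges non-inferiority by "comparing the lower limit of confidence interval for each outcome to its corresponding margin". For MFIS and the Timed Up and Go, where higher is worse, it uses the other limit: "Non-inferiority was deemed established when the upper bound was less than" the margin, printed there as −Δ.
- **Comparison standard.** The Main study, which is the superiority comparison in this document, was sized with its family-wise error held at a two-sided 0.05.

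Neither the interval nor the p-value is labelled one-sided or two-sided in the Enhancement analysis text. A 90% interval or a one-sided bound is not mentioned.

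**The concern.** One limit of a two-sided 95% interval leaves 2.5% in the tail that matters, so comparing it with a margin is a one-sided 0.025 test. A one-sided 0.05 test corresponds to one limit of a two-sided 90% interval, which is the same as a one-sided 95% bound. The sizing uses the one-sided 0.05 test. The analysis section's appeal to superiority practice points to the stricter one.

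If the stricter rule was applied, the stated 80% is not the power of the rule that decides the result. A reader who sees an outcome fail its margin would then overrate the study's chance of having shown non-inferiority where it was true. Seven outcomes have margins in the analysis section, so the missing label affects more than MFIS, although the power figure can be worked out for MFIS only.

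**Working it through.** **Inputs from the sample size section:** one-sided α = 0.05; power 80%; MFIS margin of 4 points; 55 completers; 25% attrition.

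**Input from the Enhancement analysis section:** 95% interval, one limit compared with the margin.

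**Assumptions:** true difference zero; 55 completers deliver the stated 80%; rule for MFIS read as upper limit below +4; no loss of precision from weighting.

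**1. Reproduce the plan's enrolment figure.** 55 / (1 − 0.25) = 73.3, rounded up to 74. This matches.

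The 55 cannot be re-derived from the text available, which shows neither an SD nor a comparator size. A figure in that section is not shown, so this is not counted against the plan. The check below does not need either quantity. They enter only through the standard error (SE), as does the 0.7 correlation, and the stated power fixes the SE relative to the margin.

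**2. Precision implied by the stated design.** Margin/SE = z(0.95) + z(0.80) = 1.6449 + 0.8416 = 2.4865, so SE = 4 / 2.4865 = 1.609 MFIS points.

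**3. Power under each reading of the interval.**

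| Reading of the 95% interval | Equivalent test | Power |
|---|---|---|
| One-sided bound | one-sided 0.05 | Φ(2.4865 − 1.6449) = Φ(0.8416) = 80.0% |
| One limit of a two-sided interval | one-sided 0.025 | Φ(2.4865 − 1.9600) = Φ(0.5265) = 70.1% |

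With the noncentral t distribution, the second figure is 69.8% to 70.0% for allocation ratios from 1:1 to 1:4. If 55 was rounded up from just over 54, it is at most 70.9%.

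**4. What the choice means on the MFIS scale.** At SE 1.609, the largest observed rDirectCAM disadvantage that still passes is:

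- one-sided bound: 4 − 1.645 × 1.609 = 1.35 points;
- two-sided interval: 4 − 1.960 × 1.609 = 0.85 points.

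An observed disadvantage between 0.85 and 1.35 would pass under one reading of the interval and fail under the other.

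**5. Sensitivity to the assumptions.**

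- If true power at one-sided 0.05 is 75%: Φ(1.645 + 0.674 − 1.960) = 64%.
- If it is 85%: Φ(1.645 + 1.036 − 1.960) = 76%.
- With an assumed 1.25-fold variance inflation from inverse probability weighting, margin/SE = 2.4865 / √1.25 = 2.224. Power is then Φ(2.224 − 1.645) = 72% on the one-sided reading and Φ(2.224 − 1.960) = 60% on the two-sided reading.

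**6. Scale of the shortfall.** Holding 80% at one-sided 0.025 would have taken (2.8016 / 2.4865)² = 1.27 times as many completers. That is 55 × 1.27 = 69.8, or 70 completers, and 70 / 0.75 = 93.3, or 94 enrolled, if the comparator grew in proportion. This is for scale only.

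**The case against.** **A one-sided bound fits the text.** Only one limit is ever compared with the margin, and the sizing is openly one-sided. On that reading the sections agree and no stated number is wrong. This stands, and it is why the point is conditional. It does not remove the point, because the wording that ties the interval to superiority practice points the other way and no label settles it.

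**A reader might infer that the p-value and the interval conflict and can give opposite verdicts on the same data.** The documents do not support that. The 0.05 and the 95% stand in one phrase under one standard. If both are two-sided they agree, and if both are one-sided they agree. They part only on a mixed reading, with a one-sided p-value at 0.05 beside a two-sided interval. The margin null is directional, but the plan never says that the p-value is one-sided. If both are two-sided, the mismatch with the sizing remains and power is still about 70%.

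**Neither 70% nor 80% is the power of the analysis described.** Sizing assumed ANCOVA. The analysis uses mixed models, with stabilized weighting and multiple imputation where needed. This stands. The 70% is a like-for-like restatement of the plan's own 80%, not a forecast for the weighted model.

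**The direction is conservative and the study is over:** "The study was closed on November 1, 2021". Both are true. No design decision can change, but the reported power and the reading of a failed margin still can.

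**Conclusion.** The point holds in conditional form. If the 95% interval is two-sided, which is the most natural reading, the deciding rule is a one-sided 0.025 test and the MFIS power of 55 completers is about 70%, against the stated 80%. If it is a one-sided 95% bound, 80% stands and only the label is missing.

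The 70% rests on the four assumptions listed in the working, and varying them there moved it between 60% and 76%. The printed −Δ for the MFIS upper limit is a separate question of sign. The figure applies to MFIS alone, the outcome used for sizing.

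Two stronger conclusions do not follow. Type I error is not inflated, because the two-sided reading is stricter than the stated 0.05. The 55 is not shown to be miscalculated, because it can be neither confirmed nor refuted from the text available. The point is worth correcting. Confidence is medium because the documents do not settle which interval was meant.

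**What to change.** In the Enhancement Study part of Analytical and Statistical Approaches, state the sidedness of the prespecified interval and of the p-value, at matching levels.

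- **If the rule is one limit of a two-sided 95% interval:** judge a one-sided p-value at 0.025, and restate the power in the sample size section as about 70% under the listed assumptions.
- **If the rule is a one-sided 95% bound (one limit of a two-sided 90% interval):** say so, and keep 80%.

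The choice should not be made after seeing results. If no record shows which rule was prespecified, say so and flag any outcome whose verdict depends on the choice.

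The cost on the two-sided rule is a less favourable stated power. Any p-values already judged one-sided at 0.05 would also need judging at 0.025. On the one-sided rule the change is wording only. Neither route needs new participants or refitted models.
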